6.1 Baseline Considerations

According to the protocol descriptive statistics of demographics and other baseline characteristics will be presented for all subjects in the safety analysis set and per protocol analysis set as these are the datasets used for primary response criteria.

Age and sex will be presented by country and not by centre as described in the protocol, due to too few number of subjects at most centres.

The age will be presented in three categories:

- Overall
- 12 to 14 years
- 15 to <17 years.

A table of serum cortisol concentrations at time 0, and at 30 and 60 min after ACTH challenge at baseline, although not planned in the protocol, will be produced for the per protocol analysis set.

Any abnormalities recorded during physical examination will be included in concurrent diagnoses table.

The baseline is defined as last assessment performed prior the first application of IMP.

6.1.1 Compliance

As described in the protocol, compliance with treatment instructions will be tabulated for all subjects who applied any IMP. Compliance with treatment instructions will be presented for all subjects in the safety analysis set and per protocol analysis set. Compliance is defined by number of missed days due to other reasons than cleared psoriasis in relation to treatment period. Treatment period is defined as the number of days from the treatment assignment at Visit 1 to either trial completion or early withdrawal.

The number and percentage of subjects who either did or did not comply with the trial treatment regimen will be summarized. The extent of non-compliance as categories of the percentage of applications missed will also be presented:

- No
- Yes: $\leq 10\%$ applications missed
- Yes: $> 10\%$ to $\leq 20\%$ applications missed
- Yes: $> 20\%$ to $\leq 30\%$ applications missed
- Yes: $> 30\%$ to $\leq 40\%$ applications missed
- Yes: $> 40\%$ to $\leq 50\%$ applications missed
- Yes: $> 50\%$ applications missed
- Total

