#### Treatment Period

The treatment period will last for up to 8 weeks. There are up to 5 visits: Visit 1 (day 0), Visit 2 (day 14), Visit 3 (day 28), Visit 4 (day 42) and Visit 5 (day 56). Visits 2-5 should be performed within  $\pm 2$  days of the scheduled time relative to Visit 1; if they are outside this window, the (sub)investigator should record the reason in the subject's medical record.

LEO 80185 gel will be applied once daily to scalp psoriasis lesions. Subjects should be instructed to discontinue treatment on individual lesions if/when a lesion has cleared. Subjects whose psoriasis clears after 4-week treatment will stop the investigational product and leave the trial.

Subjects who have psoriasis after 4 weeks of treatment will continue treatment for another 4-week period.

Subjects whose psoriasis clears at Visit 2 or Visit 4 according to the (sub)investigator should discontinue treatment but will stay in the study. During periods of discontinuation of treatment the subject should restart the treatment if psoriasis reappears.

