### **10.11.4 Compliance**

Compliance with treatment instructions will be tabulated for all subjects who apply any IP.

The number and percentage of subjects who comply and who do not comply with the trial treatment regimen will be summarised. The extent of non-compliance as categories of the percentage of applications missed (e.g.  $\leq 10\%$ ,  $> 10$  to  $20\%$ , etc.) will also be presented.

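### SAP 6.1.1 takes cleared days out of the missed-day count but not out of the denominator, so the banded percentage of missed applications is too low for some subjects

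*SAP*

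**What the plan says.** SAP 6.1.1 sets the measure in two sentences. The first is: "Compliance is defined by number of missed days due to other reasons than cleared psoriasis in relation to treatment period". The second is: "Treatment period is defined as the number of days from the treatment assignment at Visit 1 to either trial completion or early withdrawal". Nothing is subtracted from that period for days on which the subject was clear.

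The output is described as follows: "The extent of non-compliance as categories of the percentage of applications missed will also be presented". The bands are No, then Yes in steps of ten percentage points up to a last band above 50%. The table is planned for the safety and per protocol analysis sets. Protocol 10.11.4 asks for the same kind of output ("categories of the percentage of applications missed") and defines no denominator.

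Protocol 10.1, under Treatment Period, says: "Subjects whose psoriasis clears at Visit 2 or Visit 4 according to the (sub)investigator should discontinue treatment but will stay in the study". Such subjects resume application if the disease returns. The gel is applied once a day.

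**The concern.** With once-daily dosing, a percentage of applications missed should divide missed applications by applications that were due. On a cleared day none is due. The SAP recognises this in the numerator, where days off for clearing do not count as missed, but not in the denominator, where the same days still count. The result is neither a share of applications due nor a share of all days without gel.

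The error runs one way: it can only make the percentage smaller. At stake is whether the bands in a descriptive compliance table mean what their label says for subjects who cleared for part of the period and also missed other days.

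**Working it through.** Neither document states a compliance figure, so there is none to reproduce. The check is direct arithmetic on the definition.

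**Inputs**
- m = days missed for reasons other than clearing (SAP 6.1.1). Values below are assumed.
- T = treatment period of 28 or 56 days (Protocol Synopsis, Methodology; the ±2-day window is ignored).
- C = days off because clear. Assumed to be 14, the gap from Visit 2 to Visit 3 or from Visit 4 to Visit 5 (Protocol 10.1).
- One application per day, so one missed day is one missed application.

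**Formulas**
- As the SAP defines it: 100 × m/T
- Share of applications due: 100 × m/(T − C)
- Understatement factor: T/(T − C)

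**Factor**
- No cleared days: T/T = 1.00, no error.
- 56 days, 14 cleared: 56/42 = 1.33.
- 28 days, 14 cleared: 28/14 = 2.00.

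**Effect on the bands**

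| T | C | m | SAP: m/T | SAP band | Due: m/(T−C) | Band on applications due |
|---|---|---|---|---|---|---|
| 28 | 14 | 1 | 1/28 = 3.6% | up to 10% | 1/14 = 7.1% | up to 10% |
| 28 | 14 | 2 | 2/28 = 7.1% | up to 10% | 2/14 = 14.3% | 10 to 20% |
| 28 | 14 | 3 | 3/28 = 10.7% | 10 to 20% | 3/14 = 21.4% | 20 to 30% |
| 56 | 14 | 3 | 3/56 = 5.4% | up to 10% | 3/42 = 7.1% | up to 10% |
| 56 | 14 | 5 | 5/56 = 8.9% | up to 10% | 5/42 = 11.9% | 10 to 20% |
| 56 | 14 | 8 | 8/56 = 14.3% | 10 to 20% | 8/42 = 19.0% | 10 to 20% |

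Some subjects move up a band and others stay where they are.

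**Direction and the No/Yes split.** C cannot be negative, so T − C never exceeds T, and the SAP percentage never exceeds the percentage of applications due. With m = 0 both are zero, and with m of 1 or more both are positive. If, as the bands imply, Yes means any missed application, no subject changes between No and Yes.

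**The case against.** **The measure can be defended as it stands.** The table is about following treatment instructions. A cleared subject is told to stop, so a day off for clearing is a day on which instructions were followed. Days of non-adherence over all days in the period is then a coherent quantity. This stands as far as it goes, but that quantity is not a percentage of applications missed, which is what both documents call it. Relabelling would also remove the mismatch.

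**Few subjects may be affected.** The factor of 2.0 needs a 28-day course, clearing by Day 14 and other missed days as well. SAP Table 3 gives serum calcium totals of 104 at Week 4 and 90 at Week 8. If these totals count the subjects at each visit (an assumption), at most about 104 − 90 = 14 had a course of about 28 days. For a 56-day course with one cleared interval the factor is 1.33. This stands, and it keeps the point small.

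**Stronger readings that a reader might infer**
- *Follow-up days inflate the denominator, most of all in subjects followed for adrenal suppression.* The end point in SAP 6.1.1 is completion of the trial. Protocol 5.3 has subjects leaving after the follow-up examinations, so the words allow this reading. But the SAP is defining the treatment period. The Synopsis fixes that at 28 or 56 days, and Protocol 10.1 makes follow-up a separate period that comes after it. Compliance is collected only at Visits 2 to 5 (Protocol 3.1 and 10.6.9.4). The wording is loose, but the documents do not show that follow-up days are counted, so no bias in that subgroup follows.
- *The trial's claim to adequate exposure rests on this table.* The documents do not say so. Exposure has its own summaries: duration and subject-treatment-weeks (Protocol 10.11.5.3, SAP 6.4.1), and grams used, from weighed returned bottles (Protocol 10.6.9.3 and 10.11.5.4, SAP 6.4.2). Compliance enters neither the analysis sets in Protocol 10.11.1 nor any response criterion in 10.9 and 10.10.

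**Conclusion.** The point holds as a minor error of definition. For subjects with both a cleared interval and at least one other missed day, the banded percentage is too low by T/(T − C): 1.33 and 2.0 in the two assumed cases. All other subjects, and the No/Yes split for everyone, are unaffected.

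The cleared-day and missed-day counts above are illustrations. The documents do not give the number of affected subjects, so the effect on the whole table cannot be calculated. The conclusion also rests on the clearing rule in the protocol supplied. The SAP cites later consolidated versions (4.0 and 6.0), whose wording on this rule could not be checked. No primary or secondary result depends on the point.

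**What to change.** Replace the definition in SAP 6.1.1 with:

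Percentage missed = 100 × (days missed for reasons other than clearing) / (days from Visit 1 to the last on-treatment visit or early withdrawal, minus days off for clearing).

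Naming the last on-treatment visit as the end point, instead of completion of the trial, also removes the doubt about follow-up days.

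The cost is a change of wording and a small programming change, and the bands may look slightly worse. The numerator already requires missed days to be split by reason, so the days to subtract should be available. This needs confirming: Protocol 10.6.9.4 asks for detail only when the product was not used as prescribed, and a subject who stopped on clearing may have been recorded as compliant. The planned listing of exposure dates (Listing 5-3) may help there.

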6.2 Analysis of Efficacy

The statistical analysis of efficacy will be based on the full analysis set according to the defined response criteria in the protocol.

‘Controlled disease’ will be presented in a table by age group, the categories to be used are the same as defined in section 6.1.

Additional tables, not planned in the protocol, will be produced:

- Controlled disease (IGA on the body) at end of treatment by race
- Controlled disease (IGA on the body) at end of treatment by baseline total extent of psoriasis

Baseline for the efficacy is defined as last observation collected prior the first application of IMP, and is defined as Visit 1 for all assessments.

6.3 Analysis of Safety

The analysis of safety will be based on the safety analysis set according to the defined response criteria in the protocol, with the exception of the ACTH-challenge test which will be based on the per protocol analysis set.

Baseline for the safety analysis is defined as last observation collected prior the first application of IMP, which is Screening Visit 2.

6.4 ACTH-Challenge

The results from the ACTH-challenge will be presented as described in the protocol for the per protocol analysis set.

According to the ACTH-challenge procedure described in the protocol, samples of venous blood were to be drawn exactly 30 min and 60 min after the CORTROSYN®/SYNACTHIEN® injection, however a time deviation of +/- 10 minutes is considered acceptable as the overall value of the test is to observe substantial increases in cortisol levels and identify adrenal insufficiency up to 1 hour after the initial injection, therefore the exact timing of the incremental time points (30 and 60 minutes) is of less importance. Samples outside the acceptable deviation will not be included in the analysis. No measurements outside the acceptable deviation were observed.

6.4.1 Exposure

As described in the protocol, the duration of exposure (weeks) and extent of exposure (subject-treatment-weeks) to LEO 80185 will be summarized for the safety analysis set.

6.4.2 Drug Accountability

The amount of IMP used in grams and the average weekly amount used in grams will be tabulated for the safety analysis set, and separately for three different treatment periods (first four weeks, second four weeks, and the total treatment period).

The average weekly amount of IMP used, during the total treatment period, in defined usage categories, will be tabulated; this table was not planned in the protocol:

- <20 g/week
- 20 to <40 g/week
- \geq 60 g/week
- Total

The mean weight of full bottles, including label of IMP, is presented in Table 1 for each batch and kit number. Also the label type is given.

Table 2: Mean weight of full bottles of IMP by batch number and kit number

Batch number	Kit number	Weight of a full bottle + label (g)	Label Type
131537101	0001 - 3200	86.8 g	Booklet
P14090	3201 - 4757	86.9 g	Booklet
P14090	4758 - 5600	86.6 g	Single panel
P14090	5797-5955	87.0 g	Single panel

For each treatment period the following rules for calculating amount of IMP used will apply.

For each subject the weight of IMP used for a particular treatment period will be determined by calculating the difference between the weight of a set of full bottles dispensed and the weight of the returned bottles.

If any subjects received bottles for a particular treatment period but did not return them all, then the amount of IMP used for that treatment period will not be calculated. If any bottles are

Trial ID: LP0076-1017	Date: 16-Mar-2018	Version: 1.0 Page 11 of 27
-----------------------	-------------------	-------------------------------

not dispensed, they will not contribute to the weight of IMP used for that treatment period. If any bottles are returned with their seal unbroken, the weight of IMP used from that bottle will be assigned a value of zero. If a returned bottle weighs more than the estimated mean weight of a full bottle, it will be assumed that zero grams were used.

The average weekly amount of IMP used will be calculated for each subject as the amount of IMP used for a particular treatment period, divided by the duration (days) of the treatment period and then multiplied by 7.

6.4.3 Adverse Events

The AEs will be presented for the safety analysis set as described in the protocol.

The AEs are coded in accordance with the MedDRA dictionary version 15.1.

The number of events will be presented in all adverse events tables where number of subjects is presented.

One subject had a serious adverse event and one subject was withdrawn early from the trial due to an adverse event, therefore serious adverse events and adverse events leading to withdrawal will not be tabulated, but will be evaluated separately in the report.

Additional tables, not planned in the protocol will be produced:

- Adverse events by age group, MedDRA, primary system organ class and preferred term
- Adverse events by sex, MedDRA primary system organ class and preferred term
- Adverse events by race, MedDRA primary system organ class and preferred term
- Adverse events by baseline IGA on the body, MedDRA primary system organ class and preferred term
- Adverse events by baseline total extent of psoriasis, MedDRA primary system organ class and preferred term
- Adverse events by IMP usage (<40 g/week, ≥40 g/week), MedDRA primary system organ class and preferred term.

Adverse events will be presented separately for subjects using at least 40 g per week of IMP during the total treatment period and for those using less than 40 g per week of IMP during the total treatment period.

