In this trial, treatment for up to 8 weeks is expected to be safe. The application area of LEO 80185 gel for subjects in the trial is expected to decrease with time as their psoriasis decreases in severity. Thus, the amount of investigational product required is expected to be less by the end of the trial. Adrenal function will be assessed by an ACTH-challenge test before, during, and at the end of trial treatment. This test involves injecting a synthetic subunit of ACTH (CORTROSYN®) into the subject, and measuring the cortisol produced by the adrenal glands 30 and 60 minutes after the injection.

The use of CORTROSYN® in this trial will be in keeping with that detailed in the US Prescribing Information ([Appendix III](#)); therefore this is expected to be of low risk.

The risk of hypercalcemia due to systemic absorption of the calcipotriol component of LEO 80185 gel is expected to be low when the medication is used in the doses specified in the trial. Any potential effects of LEO 80185 gel on calcium metabolism will be assessed by measurement of the concentrations of serum calcium and -phosphate and plasma parathyroid hormone (PTH) and the urinary calcium-, phosphate-, and creatinine excretion based on collection of 24-hour urine and the calcium:creatinine and phosphate:creatinine, ratios will be calculated before, during and at the end of treatment.

The expected total blood volume collected will be approximately 46.5 ml for subjects performing HPA axis assessments and 31.5 ml for subjects not performing HPA axis assessments. This excludes any follow-up assessment of abnormal values. Topical anaesthetic will be provided at study sites to decrease discomfort and pain for the subjects when having placed catheters at the (sub)investigator's discretion.

Recruitment for the trial will be continued until 100 subjects are available for evaluation of calcium metabolism. This includes the 30 subjects (in the US) without adrenal suppression at baseline who is to undergo ACTH-challenge test at end of treatment (Visit 3 or 5).

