### **10.11.7 General Principles**

Categorical data will be summarised using the number and percentage of subjects in each category. Continuous data will be summarised using the mean, standard deviation (SD), median, minimum and maximum values.

All confidence intervals will be two-sided and presented with 95% degree of confidence, unless otherwise stated.

The data recorded during the course of the trial will be presented in individual data listings, according to ICH E3.

For tabulations on changes from baseline, baseline will be defined as the last assessment performed before application of IP.

The end of treatment value for a particular parameter will be defined as the last value recorded for that parameter up to and including Visit 5 (Week 8). However, for laboratory parameters this will be the last value recorded after baseline (SV2) up to and including Visit 5.

All efficacy data will be tabulated by visit using an observed cases approach (i.e. involving only those subjects who attended each specific visit) except for the tabulation of end of treatment values.

All laboratory data will be tabulated by visit using an observed cases approach except for the tabulation of end of treatment values which will be presented for the primary response criteria.

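### The adverse event tables by baseline severity, baseline extent and gel use have no time denominator, although subjects clear at Week 4 are observed for about half as long as the rest

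*SAP*

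**What the plan says.** **Length of observation.** Protocol 10.1, Treatment Period: "Subjects whose psoriasis clears after 4-week treatment will stop the investigational product and leave the trial". Subjects who still have psoriasis at that point are treated for four more weeks. Visit FU1 does not even this out. Under Protocol 10.1, Follow-up, it takes place only for an unresolved event that may be drug related, or for raised albumin-corrected calcium.

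**What the AE tables count.** Protocol 10.11.5.1 counts subjects with each type of event. Protocol 10.11.7 adds: "Categorical data will be summarised using the number and percentage of subjects in each category". SAP 6.4.3 adds: "The number of events will be presented in all adverse events tables where number of subjects is presented".

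**The subgroup tables at issue.** Among the tables that SAP 6.4.3 adds beyond the protocol are:
- "Adverse events by baseline IGA on the body, MedDRA primary system organ class and preferred term" (Table 3-45)
- "Adverse events by baseline total extent of psoriasis, MedDRA primary system organ class and preferred term" (Table 3-46)
- a split by gel use at 40 g per week: "Adverse events will be presented separately for subjects using at least 40 g per week of IMP during the total treatment period", and likewise for those using less (Table 3-47)

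**Exposure.** SAP 6.4.1: "the duration of exposure (weeks) and extent of exposure (subject-treatment-weeks) to LEO 80185 will be summarized for the safety analysis set". This is one table for the whole set (Table 3-28). Neither document plans exposure by subgroup, AE rates per unit of time, or an AE table restricted to the first four weeks.

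**Gel use.** SAP 6.4.2 divides the grams used in a period by its length in days and multiplies by 7. Protocol 5.3 anticipates that "the amount of investigational product required is expected to be less by the end of the trial".

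**The concern.** A subject followed for four weeks has less opportunity to report an event than one followed for eight. Who leaves at Week 4 depends on response. It is reasonable to expect, though the documents do not state it, that milder or less extensive disease clears sooner. The amended criteria in SAP Table 1 make this more relevant. Subjects outside the HPA and PK subset may now enter with mild disease and with body involvement from 3%, so baseline severity and extent vary more widely.

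Gel use has a second link to time. If consumption falls over the trial, the average over the total treatment period depends on how long the subject stayed. Follow-up length then affects both the usage group and the chance of an event.

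Table 3-47 is the only listed AE table by amount of gel used, and readers will set its two columns side by side. They cannot see from the planned output whether the columns had similar follow-up.

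**Working it through.** **1. The plan's own AE figure.** Protocol 10.3 gives about 4% as the upper exact two-sided 95% limit when 0 of 100 subjects have an event. Check: 1 − 0.025^(1/100) = 3.62%. It reproduces. It is a per-subject figure and takes no account of follow-up time.

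**2. How many left early.** The totals in SAP Table 3 for albumin-corrected calcium, read as subjects still in the trial, are 107 at SV2, 104 at Week 4 and 90 at Week 8. The rows add up (99 + 5 = 104; 87 + 3 = 90). Leavers between Week 4 and Week 8: 104 − 90 = 14, or 13.5% of 104. This is a ceiling for exits due to clearance. It also includes withdrawals and any subject stopped for low cortisol at Week 4 (Protocol synopsis, Methodology).

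**3. Artefact from time alone.** The documents give neither the AE risk nor the subgroup sizes, so both are assumed. Take the same constant hazard in both groups and let p8 be the 8-week risk. Then:
- 4-week risk: p4 = 1 − √(1 − p8)
- crude percentage in a group of n with k leavers: [k·p4 + (n − k)·p8] / n

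For p8 = 20%, p4 = 10.6%. For p8 = 40%, p4 = 22.5%. Each cell below shows the group with more leavers against the other group, for 104 subjects in total. The first row has equal shares of leavers.

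| Where the 14 leavers fall | p8 = 20% | p8 = 40% |
|---|---|---|
| 7 in each group of 52 | 18.7% v 18.7%, gap 0 | 37.6% v 37.6%, gap 0 |
| all in one group of 52 | 17.5% v 20.0%, gap 2.5 | 35.3% v 40.0%, gap 4.7 |
| 10 in a group of 30, 4 in the other 74 | 16.9% v 19.5%, gap 2.6 | 34.2% v 39.1%, gap 4.9 |
| all in a group of 20 | 13.4% v 20.0%, gap 6.6 | 27.8% v 40.0%, gap 12.2 |

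Worked cell: (14 × 10.56% + 38 × 20%) / 52 = 17.5%.

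**4. In subjects.** The expected shortfall is 14 × (p8 − p4). That is 14 × 0.0944 = 1.3 subjects at 20% and 14 × 0.1746 = 2.4 subjects at 40%. Over all 104 it amounts to 1.3 and 2.4 points.

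**5. With a time denominator.** The rate is −ln(1 − p8)/8, or 2.79 per 100 subject-weeks at 20% and 6.39 at 40%. It is the same in both groups, so every gap in the table disappears.

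**6. The usage category.** Suppose a subject uses 45 g per week in Weeks 1 to 4 and 30 g per week in Weeks 5 to 8 (assumed values). The average is (4 × 45 + 4 × 30) / 8 = 37.5 g, which falls below 40 g. A subject with the same first four weeks who leaves at Week 4 averages 45 g and falls in the upper group. Dividing by duration does not prevent this, because the average is taken over a different stretch of a falling curve.

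**The case against.** The strongest reply is that little depends on these tables. They are additional and descriptive, they carry no test or confidence interval, and they change no response criterion. At most 14 subjects are involved. Exposure dates and AEs are listed by subject (Listings 5-3 and 7-5), so timing can be checked. All of this stands and sets the weight of the point. It does not remove the point, because someone reading the tables sees the columns and not the follow-up behind them.

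A reader might infer more than the documents support:

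- *That the SAP compares groups to isolate a drug effect.* It presents them separately. With a single arm, a difference by baseline severity or extent would not be a drug effect even with equal follow-up.
- *That the distortion is large.* Suppose 40% of one group and 10% of the other left at Week 4. With 14 leavers, 0.4n + 0.1(104 − n) = 14 gives n = 12, so that picture needs groups of 12 and 92.
- *That longer follow-up pushes subjects into the lower-use group.* This holds only for the same pattern of use. Subjects who stay longer may have more disease and use more gel, which works the other way.
- *That the pooled adverse drug reaction percentage is invalid.* It is the risk under the regimen studied, which is up to eight weeks with exit at Week 4 if clear.
- *That the tables by age, sex and race need the same change.* Nothing in the documents ties those factors to early exit.

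**Conclusion.** The point holds as a modest weakness of presentation in Tables 3-45 to 3-47. Their percentages and counts ignore a follow-up time that depends on response, and the usage grouping depends on that time as well.

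The artefact lies between 0 and about 2.5 to 4.7 percentage points for two equal groups. It is larger only if the leavers are concentrated in a small subgroup. These figures rest on a constant hazard, assumed 8-week risks of 20% to 40%, and 14 leavers as an upper bound. The number clear at Week 4 in each subgroup is not given, so the actual size cannot be stated. The net direction in the gel-use table cannot be determined from the documents.

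**What to change.** In Tables 3-45 to 3-47, add for each group the subject-treatment-weeks and the events per 100 subject-treatment-weeks beside the existing counts, and label them descriptive. State how weeks off gel are counted for subjects who clear at Visit 2 or Visit 4 but remain in the trial.

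Optionally, add a supportive version of Table 3-47 with usage groups defined on the first four weeks, an amount SAP 6.4.2 already calculates, and with events starting in those weeks. It should not replace Table 3-47, because it sets aside events after Week 4 although 90 of 104 subjects continued.

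The cost is a few columns from exposure and event data already produced. The downside is that rates assume a roughly constant hazard and are unstable for rare preferred terms, so the counts should stay alongside. The pooled tables and those by age, sex and race can remain as planned.
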